7.0 TREATMENT PLAN/INTERVENTION

Patients will be randomized with equal probability to receive daily treatment with Z-Endoxifen HCl or tamoxifen. Treatment on Arms I and II will continue until disease progression or unacceptable adverse event.

Protocol treatment is to begin \leq 14 days of registration/randomization in order to allow for Z-Endoxifen HCl to arrive for patients assigned to Arm I.

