13.1.3 Sample Size, Accrual Time and Study Duration

This trial was designed under the assumption that the median progression-free survival time among patients receiving tamoxifen is 3.0 months. Disease assessments in this trial are made at a frequency that is half the hypothesized median of the tamoxifen arm. Stone et al [41, 42] (2, 3) found that when disease assessments are made at a frequency that is half the control median, the difference in power between the log-rank test (with documented progression times) and generalized log-test with interval censored data was < 3%. As such we will determine the sample size assuming a log-rank test will be used with one-sided alpha=0.10 and power=95% so that the interval censored approach with the generalized log-rank test will have a power of > 90%.

With a sample size of 80 eligible patients (40 per treatment arm randomized in equal numbers) over a 15 month period and followed at least another 9 months after the close of enrollment before analysis is undertaken, a one-sided alpha=0.10 generalized log-rank test will have at least a 90% chance of detecting a 50% decrease in hazard of disease progression with Z-Endoxifen HCl relative to tamoxifen.

That corresponds to being able to detect an increase in the median PFS time from 3.0 months with tamoxifen to 6.0 months with Z-Endoxifen HCl.

An additional 14 patients will be screened to account for ineligible patients (tumors that are ER negative on biopsy) and those who cancel participation prior to starting treatment.

As of November 1, 2016, 24 (30%) of the 81 patients enrolled on this trial were found to have ER negative and/or HER2 positive breast cancer, a second primary cancer, or benign disease, making them ineligible. Therefore, the number of patients needed to be screened to obtain 80 eligible patients will be increased from 94 to 115 patients.

The efficacy analysis will be conducted when at least 72 patients have provided documentation of local, regional or distant disease progression or death without progression of disease.

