13.1.6 Secondary Clinical Endpoints

13.1.6.1 Adverse Events

Per CTEP Version 4.0 of the NCI CTCAE, an adverse event (AE) is any unfavorable and unintended sign (including an abnormal laboratory finding), symptom, or disease temporally associated with the use of a medical treatment or procedure that may or may not be considered related to the medical treatment or procedure. All grade 2, 3, 4 or 5 adverse events will be documented and assigned an attribute by treating clinician as to its relationship to treatment.

Note: Serious adverse events will be reported on CTEP-AERS using CTCAE v5.0.

For a given AE, the proportion of patients on each treatment arm who report developing a grade 2-5 of this AE will be determined.

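### Adverse events are summarised only as crude proportions per arm, so if Z-Endoxifen prolongs PFS, events that accrue over time could look more frequent on it at equal monthly toxicity

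*Combined protocol and SAP*

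**What the plan says.** Section 13.1.6.1 plans that, for a given AE, "the proportion of patients on each treatment arm who report developing a grade 2-5 of this AE will be determined". The statistical section plans no exposure-adjusted rate, time-to-first-event estimate, fixed-window proportion or summary of treatment duration. The by-arm descriptive list in section 13.1 includes length of follow-up and treatment acceptance, but not time on drug.

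Three other places bear on this:

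- **Time on treatment.** Section 7.0: "Treatment on Arms I and II will continue until disease progression or unacceptable adverse event". The calendars in sections 5.1 and 5.2 schedule an AE assessment on day 1 of every cycle and at progression or discontinuation.
- **Design alternative.** Section 13.1.3 sizes the trial for "an increase in the median PFS time from 3.0 months with tamoxifen to 6.0 months with Z-Endoxifen HCl".
- **Grouping and crossover.** Section 13.1 keeps patients in their randomised group whatever they received and for however long. Section 5.2 lets tamoxifen patients move to Z-Endoxifen at progression and continues AE assessment through that phase. No rule says under which heading those later AEs are counted.

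**The concern.** A patient can contribute an on-treatment AE only while on treatment and being assessed. When treatment lasts until progression, that time is itself an efficacy outcome. The proportion ever affected then mixes how toxic a drug is per month with how long it holds the disease.

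Safety is the first secondary objective (2.2.1). The proportions will be tabulated by arm in a randomised trial and are likely to be read side by side. Without treatment duration or a time-based summary, a reader could not tell a more toxic drug from one that patients stayed on longer.

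**Working it through.** **The plan's own figure first.** Section 13.1.3 sizes the trial "assuming a log-rank test will be used with one-sided alpha=0.10 and power=95"% for a hazard ratio of 0.5, with analysis at 72 events. Events needed = 4(1.282 + 1.645)² / (ln 2)² = 71.3, so 72. Power at 72 = Φ(√72 × 0.693/2 − 1.282) = Φ(1.659) = 95.1%. With exponential PFS, 40 per arm, uniform 15-month accrual and 9 further months, expected events are 38.6 + 33.3 = 71.9. The plan is consistent, so its medians and follow-up can be used to project time on treatment.

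**Inputs from the plan.** Medians of 3.0 and 6.0 months give progression hazards μ = ln 2/3 = 0.231 and ln 2/6 = 0.116 per month. Follow-up is uniform on 9 to 24 months.

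**Assumptions.** The documents give no AE hazard, crossover share or time on crossover treatment. I take treatment to end at progression and a first-AE hazard λ that is identical in the two arms.

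**Time on randomised treatment.** The mean 1/μ is 4.3 versus 8.7 months (ratio 2.0). With the 24-month cut-off it is 4.2 versus 7.2 months (ratio 1.7).

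**Crude proportion, constant hazard.** Without a cut-off it is λ/(λ+μ). With follow-up f it is the average over f of λ/(λ+μ) × (1 − e^(−(λ+μ)f)).

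| λ per month | Tamoxifen | Z-Endoxifen |
|---|---|---|
| 0.02 | 8% | 13% |
| 0.05 | 17% | 28% |
| 0.10 | 30% | 44% |

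**When the gap is small.** The hazard is set so that tamoxifen shows 20%, with no cut-off.

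| Condition | Tamoxifen | Z-Endoxifen |
|---|---|---|
| AE risk in cycle 1 only | 20% | 20.8% |
| AE risk in first 6 weeks only | 20% | 21.5% |
| AE risk in first 3 months only | 20% | 23.2% |
| Constant risk, time on drug 1.25 times longer | 20% | 23.8% |
| Constant risk, time on drug 1.5 times longer | 20% | 27.3% |
| Constant risk, equal PFS | 20% | 20% |

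**Crossover.** A constant-hazard 20% on tamoxifen means λ = 0.0578, and Z-Endoxifen then shows 33.3% (no cut-off). Suppose crossover AEs count under tamoxifen, at the same hazard and with an assumed median of 3 months on crossover. If a share c crosses over, the tamoxifen proportion is 0.20 + 0.80 × c × 0.20. That is 28.0% at c = 50%, 32.0% at 75% and 36.0% at 100%. The last exceeds 33.3%, so the direction reverses.

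**What the alternatives would show (24-month cut-off).**

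- *First events per patient-month at risk, time at risk ending at the first event:* at λ = 0.10, 10.0 per 100 in both arms.
- *The same numerator over all months on treatment:* at λ = 0.10, 7.2 versus 6.2 per 100, which falsely favours Z-Endoxifen.
- *Either rate when AEs occur only in cycle 1:* even with time at risk ending at the first event, 6.0 versus 3.6 per 100, because the later event-free months dilute the longer arm.
- *Incidence by 4 cycles (84 days, 2.76 months), censored at end of treatment:* at λ = 0.05, 1 − e^(−0.05 × 2.76) = 12.9% in both arms. The raw proportion in the same window is 9.6% versus 11.1%.

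**The case against.** The strongest reply is that no between-arm AE comparison is planned. Objective 2.2.1 concerns the safety profile of each agent, whereas 2.2.2 asks expressly whether response differs. The proportion affected over a course of treatment to progression is a legitimate descriptive quantity. The safety stopping rule in section 13.1.7 also applies to each arm separately. This stands as a reason to keep the crude proportion. It does not make that proportion sufficient as the only summary, because the by-arm figures invite comparison and no treatment duration accompanies them.

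Second, the gap is modest against chance. With 40 per arm, 17% versus 28% is about 7 versus 11 patients, and the standard error of the difference is about 9 points. That is true, but the gap is systematic and would recur across every AE that accrues steadily.

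Third, a reader might infer that equal toxicity would simply look much worse on Z-Endoxifen. The documents do not support that. It needs the PFS benefit to be real, AEs to accrue steadily, and tamoxifen AEs to stop counting at crossover. None of these is established. Section 1.6 reports steady-state troughs by day 7, so early onset is plausible for some AEs, and sections 13.1 and 5.2 leave the crossover count open. A reader might also infer that the AE table decides further development. Section 13.1 defines promise by PFS and states no such role for it.

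**Conclusion.** The concern holds in conditional form. The only planned AE summary mixes toxicity with time on treatment, and the design alternative itself implies 1.7 to 2.0 times as long on Z-Endoxifen. At an equal constant AE hazard that gives 8% versus 13%, 17% versus 28% or 30% versus 44%, for assumed hazards of 0.02, 0.05 and 0.10 per month. For AEs confined to the first cycles the gap is about 1 to 3 points at 20%, and with equal PFS there is none. Until the counting window at crossover is stated, the direction of any distortion is undetermined.

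The sizes rest on exponential times, treatment ending at progression, and AE and crossover inputs that the documents do not give. The primary analysis is unaffected. This is an improvement that should be made to a secondary objective.

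**What to change.** In section 13.1.6.1, keep the crude proportion and add the following:

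1. **Counting window.** Count AEs on randomised treatment only. Cut tamoxifen-arm AEs at crossover and report the crossover phase in a separate table.
2. **Treatment duration.** Report time on randomised treatment by arm beside the AE table.
3. **Time to first grade 2-5 event for each AE**, censored at the end of randomised treatment, shown as (a) the cumulative incidence at a fixed early time such as 4 cycles, and (b) first events per patient-month at risk, with time at risk ending at the first event. Give 90% intervals, in line with section 13.1.6.2.
4. **Reading rule.** Read between-arm differences from (a) and (b) together. The rate alone misleads for early-onset AEs (6.0 versus 3.6 per 100 above), and the early estimate alone misses late ones.

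The cost is SAP wording and a few extra table columns. AEs are already assessed every cycle and dosing dates are kept in the medication logs (section 7.4, Appendix III), so no new visit, sample or patient is needed. Two limits should be stated. The rate assumes a roughly constant hazard. Censoring at end of treatment assumes that stopping is unrelated to the risk of that AE, which is doubtful where treatment stops for toxicity.

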2.2 Secondary Objectives

- 2.2.1 To assess the safety profile of each of these agents in this patient population.
- 2.2.2 To assess whether the tumor response rate (as determined using the RECIST criteria) among those randomized to Z-endoxifen HCl differs from that among those randomized to tamoxifen.
- 2.2.3 To estimate the median progression-free survival time for those who receive Z-Endoxifen HCl after disease progression with tamoxifen.

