8.2.2 Z-Endoxifen HCl

If a grade 3 or 4 lymphopenia, thrombocytopenia, or hypertriglyceridemia, hold Z-Endoxifen HCl therapy until toxicity resolves to < grade 2. Reduce dose to 40mg daily. If the toxicities do not resolve to ≤ grade 1 or baseline severity within 21 days (1 cycle), treatment is to be discontinued and the patient will go to event monitoring. If toxicity recurs, treatment is to be discontinued.

If a grade 3 or 4 non-hematologic event that is attributed to Z-Endoxifen HCl occurs, hold therapy until toxicity resolves to ≤ grade 1 or back to baseline (if baseline is grade 2) and reduce dose to 40mg daily. If the toxicities do not resolve to ≤ grade 1 or baseline severity within 21 days (1 cycle), treatment is to be discontinued and the patient will go to event monitoring.

The prompt reporting of adverse events is the responsibility of each investigator engaged in clinical research, as required by Federal Regulations. Adverse events must be described and graded using the terminology and grading categories defined in the NCI’s Common Terminology Criteria for Adverse Events (CTCAE), Version 4.0. The CTCAE is available at:

http://ctep.cancer.gov/protocolDevelopment/electronic_applications/ctc.htm. Attribution to protocol treatment for each adverse event must be determined by the investigator and reported on the required forms, using the codes provided.

Note: Serious adverse events will be reported on CTEP-AERS using CTCAE v5.0.

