10.1.7 Adverse events

The most common adverse effects of Z-Endoxifen HCl have been mostly grades 1-2 hot flashes (50%), anemia (25%), fatigue (25%), lymphocyte count decreased (22%), nausea (19%), platelet count decreased (19%), hypertriglyceridemia (16%), irritability (16%), anorexia (13%), AST increased (13%), edema limbs (13%), and WBCs decreased (13%).

Thromboembolic event (grades 3-4) and hypertriglyceridemia (grade 4) have also been reported.

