13.1.7 Monitoring

The study chair, the faculty statistician and the executive officer will review the trial data every 3 months to identify accrual, toxicity, and endpoint problems that might be developing. The faculty and secondary statistician will prepare a report containing accrual, adverse events, and efficacy data which will be submitted to the ALLIANCE Data and Safety Monitoring Board on a semi-annual basis.

Safety stopping rules will be applied to each treatment arm separately. If 3 or more of the first 10 patients randomized to a given treatment arm or 30% or more of patients randomized to that treatment arm thereafter develops a grade 4 hematologic or non-hematologic toxicity possibly, probably or definitely related to treatment, the enrollment to the trial will be temporarily suspended so that all AE data can be examined. The study chair and the faculty statistician will formulate a trial recommendation to present to the ALLIANCE DSMB and CTEP for approval.

The study chair and the faculty statistician will formulate a trial recommendation to present to the ALLIANCE DSMB and CTEP for approval.

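### The final adverse event summary merges grades 2 to 5 within each AE term; outside the grade 4 monitoring rule, no grade 3 or higher rate by arm is planned

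*Combined protocol and SAP*

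**What the plan says.** Safety is a secondary objective. Section 2.2.1 reads "To assess the safety profile of each of these agents in this patient population".

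For data capture, Section 13.1.6.1 states "All grade 2, 3, 4 or 5 adverse events will be documented and assigned an attribute by treating clinician", so individual grades and attribution are both available. For analysis, the same section says only that, for a given AE, "the proportion of patients on each treatment arm who report developing a grade 2-5 of this AE will be determined". It names no maximum-grade table, no grade 3 or higher proportion, no treatment-related proportion and no interval. Tumor response, in Section 13.1.6.2, does get a 90% binomial confidence interval.

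Section 13.1.7 adds a monitoring rule applied to each arm separately. It begins "If 3 or more of the first 10 patients randomized to a given treatment arm or 30% or more of patients randomized" and counts a patient who "develops a grade 4 hematologic or non-hematologic toxicity possibly, probably or definitely related to treatment". Meeting it suspends enrollment so that AE data can be reviewed. The same section also provides for reports to the monitoring board: "The faculty and secondary statistician will prepare a report containing accrual, adverse events, and efficacy data". It does not say how AEs will be broken down by grade.

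On what is already known, Section 10.1.7 describes mostly grade 1-2 effects and then adds: "Thromboembolic event (grades 3-4) and hypertriglyceridemia (grade 4) have also been reported". Section 1.6 says the same, and reports a pulmonary embolism as the one cycle 1 dose-limiting toxicity seen in the phase I trial.

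**The concern.** A safety profile has to show how severe events were as well as how often they occurred. The known Z-Endoxifen harms of most interest are at grades 3 and 4. Followed exactly, the stated summary puts a patient with grade 2 hypertriglyceridemia and a patient with grade 4 hypertriglyceridemia in the same numerator. Two arms with equal grade 2-5 proportions for one AE term, but different severity, would give the same reported result.

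The severity cut would then be chosen after the data are seen, or not reported at all. At stake is the description of severe toxicity by arm for objective 2.2.1. The PFS analysis, the sample size and the conduct of the trial are not affected.

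**Working it through.** **Plan's own figures.** The AE section states no rate, precision or sample size, so it has no figure to reproduce. The one AE threshold in the plan, in 13.1.7, is consistent with itself: 3/10 = 30%, the same as the later limit.

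**Inputs.**
- Denominator: 40 patients per arm (13.1.3). Evaluable patients are those who are eligible, consented and started on treatment (13.1).
- Final AE summary: grade 2-5, per AE term and arm (13.1.6.1).
- Monitoring rule: related grade 4, all terms together, per arm (13.1.7).
- Severe AE counts: none are given by arm, so every count below is an assumption.

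**Step 1. What each planned quantity separates.**

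| | Final summary, 13.1.6.1 | Monitoring rule, 13.1.7 |
|---|---|---|
| Separates AE terms | Yes | No |
| Separates grade 2 from 3 or higher | No | Counts grade 4 only |
| Uses attribution | No | Yes |
| Purpose | Final description | Enrollment suspension |

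Neither one gives a grade 3 or higher rate for a named AE.

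**Step 2. Hypothetical masking within one AE term.** Suppose 12 of 40 patients in each arm have grade 2-5 of the same AE.
- Arm A: 11 with maximum grade 2 and 1 with grade 3-5.
- Arm B: 6 with maximum grade 2 and 6 with grade 3-5.
- Planned summary: 12/40 = 30% in both arms.
- Grade 3-5: 1/40 = 2.5% against 6/40 = 15%.

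The monitoring rule need not show this either. If the six events in arm B are all grade 3, none is counted. If all six are related grade 4 and there are no other grade 4 toxicities, 6/40 = 15% is below the 30% limit. The rule would act only if at least three of the six fell among the first ten patients, or if the running proportion reached 30% later.

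**Step 3. How sensitive the early monitoring rule is.** With true related grade 4 rate p, the chance of 3 or more in the first 10 is 1 − Σ(k=0 to 2) C(10,k) p^k (1−p)^(10−k).
- p = 5%: 1.2%
- p = 10%: 7.0%
- p = 20%: 32.2%
- p = 30%: 61.7%

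It is a coarse check on grade 4 toxicity and does not estimate a rate for any AE.

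**Step 4. What the added proportion would deliver.** Exact (Clopper-Pearson) 95% intervals at n = 40:
- 0/40 = 0% (0 to 8.8%)
- 2/40 = 5% (0.6 to 16.9%)
- 4/40 = 10% (2.8 to 23.7%)
- 6/40 = 15% (5.7 to 29.8%)

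The chance of seeing at least one such event in 40 patients is 1 − (1−p)^40: 33% at p = 1%, 70% at 3%, 87% at 5% and 99% at 10%.

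The intervals are wide. Even 1/40 against 6/40 gives a two-sided Fisher p of about 0.11. The gain is therefore in description with stated uncertainty; a formal comparison of arms would have little power.

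**The case against.** The strongest reply is that severe toxicity is far from ignored, and much of that stands.

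- **A reader might infer that the grade 2-5 proportion is the only planned AE statistic, or that no severe-toxicity rate is produced.** Section 13.1.7 contradicts both. It requires a per-arm count and proportion of related grade 4 toxicity during accrual. That narrows the gap without closing it, because the rule pools all terms, leaves out grade 3 and unrelated events, and is not a final analysis.
- **A reader might infer that attribution is collected and never used.** It is used in 13.1.7 and in the dose modification text of 8.2.2. It is absent only from the final summary in 13.1.6.1.
- **A reader might infer that a severe thromboembolic event is swamped by common grade 2 laboratory changes.** Pooling is within one AE term, so the two are never merged. The documents give no grade 2 thromboembolic rate and no grade split of hypertriglyceridemia, so actual masking cannot be shown for either.
- **A reader might want the table to line up with the hold rules, such as "If a grade 3 or 4 non-hematologic event that is attributed to Z-Endoxifen HCl occurs" in 8.2.2.** Those rules govern individual patients. They are not population thresholds, and an end-of-study table need not be read against them.
- **Severe events are seen elsewhere.** The study team reviews toxicity every 3 months and the monitoring board receives AE data twice a year. Grade 4 and 5 serious events need notice within 24 hours, and every death on study is reported (Sections 9.2 and 13.1.7). This protects patients during the trial, but it does not define what the final analysis reports by arm.
- **Grades are recorded, and nothing forbids a fuller table.** That is correct. It makes the remedy easy, but it does not pre-specify the severity cut. If a grade-by-grade table was intended, the sentence does not say so.

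**Conclusion.** The point holds in a limited form. Section 13.1.6.1 commits to one final AE summary, which does not distinguish grade 2 from grade 3-5 within an AE term. Apart from the all-term, related grade 4 suspension rule, no grade 3 or higher rate by arm is planned for objective 2.2.1, although severe events are already known for the study drug.

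The size cannot be computed from the documents. The 2.5% against 15% contrast is hypothetical, within one AE term, and assumes 40 evaluable patients per arm. The conclusion itself rests only on the wording of 13.1.6.1 and 13.1.7. This is a gap in the specified analysis. Data collection and safety oversight during the trial are not at fault, and correcting it is a worthwhile improvement at almost no cost.

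**What to change.** In the closing sentence of 13.1.6.1, specify that:
- each AE is tabulated by maximum grade per patient and by arm;
- the per-arm proportion with grade 3 or higher is reported for each AE and for any AE, both regardless of attribution and for events at least possibly related to treatment, with exact 95% confidence intervals;
- the grade 2-5 proportion is kept as an additional column.

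The tables are descriptive, and no test between arms is needed. The cost is a few lines of plan wording and some extra columns from data already collected. No dose, hold or stopping rule changes.

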13.1.6.2 Tumor Response Rate by study arm

The tumor response rate is defined as the 100% time the number of patients with a CR or PR (as defined by the RECIST criteria) on 2 consecutive evaluations at least 6 weeks apart divided by the total number of eligible patients who began study treatment. A 90% binomial confidence interval will be constructed for the true response rate.

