1.3.4 Tamoxifen

The activity of TAM in the metastatic setting following AI failure has been evaluated in several studies. Osborne et al conducted a randomized phase II trial evaluating the activity of tamoxifen +/- gefitinib in either hormonally naïve (stratum I) or patients who relapsed on AI (stratum II). In stratum II, for patients randomized to TAM alone, the objective response rate was 0% and progression free survival 7.0 month [23]. In the TAMRAD study, patients who had failed a non-steroidal AI were randomized to either tamoxifen alone or tamoxifen + everolimus. Notably, in this trial, time to progression was 4.5 months in patients randomized to the tamoxifen arm with a 6 month complete benefit rate (complete, partial or stable disease) of 42%.

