5.1 Study Arm 1 Z-Endoxifen HCl

	Prior to pre-registration	Pre-registration Period (any time during days -28 to -1)	Days 1 of each treatment cycle*	At PD or discontinuation of protocol therapy**
Tests & Observations				
History and physical, weight, PS	X		X	X
Height	X			
Pulse, Blood Pressure	X		X	X
Adverse Event Assessment			X	X
Patient Medication Log			X(1)	X(1)
Registration Fatigue/Uniscale Assessment		A		
Standard of care biopsy of either locally recurrent or metastatic breast cancer is required for determination of ER, PR and HER2		B		
Laboratory Studies				
AST, creatinine, Total Bilirubin	X	X	X	X
Complete Blood Count, Differential, Platelets	X	X	X	X
Albumin, Alk Phos, ALT, calcium, glucose, phosphorous, sodium, potassium,		X	X	X
Fasting lipid profile (total Cholesterol, LDL, HDL, triglycerides)		C	C	
Imaging Tumor Measurements/Evaluation of Indicator Lesions				
CT/MRI		D, E, F	D,	D, E
Bone Scan/PET-CT scan		D, E, F	E	E
Correlative Studies: For Patients who consent to participate				
Tissue and Blood samples	See Sections 6.0 and 14.0 .			

* Cycle length is 21 days. Labs completed prior to registration may be used for day 1 of cycle one tests if obtained ≤ 21 days prior to treatment. For subsequent cycles, labs, scans, tests and observations may be obtained no more than +/- 3 days prior to day 1 of treatment.

** After treatment discontinuation, patients will be followed yearly for a maximum of 5 years from study registration/randomization (see Section [12.3](#)).

1. Medication Log must begin on the day the patient begins study medication and must be completed per protocol until treatment discontinuation (see Section [7.4](#)).

- A. To be completed after Pre-registration and prior to treatment, and will take approximately a minute to complete (see Section [1.8](#) and [Appendix I](#)).
- B. A standard of care biopsy of locally recurrent or metastatic breast cancer during the pre-registration period is required to confirm ER, PR and HER2 status by an institutional/local pathologist and for submission of a research block for optional correlative studies. **However**, if a prior biopsy was performed on a locally recurrent/metastatic site within 90 days of pre-registration, and no anti-cancer therapy was administered during that time period, that specimen can be used for confirmation of ER/PR/HER2 and for submission of tissue for optional correlative studies.

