- C. Lipid profile is required at Pre-registration (baseline), cycles 2, 4 and 8 and thereafter at the discretion of the treating physician.
- D. Acceptable imaging modalities for measurable disease include: a CT, spiral CT, MRI, and chest x-ray. A FDG-PET scanning is allowed to complement CT scanning in assessment of progressive disease.
- E. Tumor measurements are required during the pre-registration period (days -28 to -1), at completion of cycles 2, 4, and 6 (approximately, every 6 weeks) then every 4 cycles (approximately every 3 months) thereafter until disease progression, as determined in Section [11.0](#). The same imaging method utilized at baseline must be used at all disease assessments and must include all target and non-target lesions recorded at baseline.

For patients without bone metastases, bone scans after the baseline bone scan are at the discretion of the treating physician. See Section [11.0](#) for acceptable modalities for tumor imaging.

For patients with non-measurable bone only disease, follow-up imaging either with PET/CT or bone scan should be performed at the time of tumor assessment. The same imaging method utilized at baseline must be used at all tumor assessments.

- F. Need not be repeated if performed before pre-registration period, but not more than 28 days prior to registration.

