7.1 Arm I Z-Endoxifen HCl

Agent	Dose	Route	Day	Retreatment Cycle
Z-Endoxifen HCl	80 mg	Oral (2 x 40mg capsule)	Days 1-21	Every 21 days (+/- 3 days)

1. Patients will take Z-Endoxifen HCl on an empty stomach (1 hour before or 2 hours after meals).
2. Patients should be instructed that the Z-Endoxifen HCl should be refrigerated. The Z-Endoxifen HCl should be dispensed with a cooler pack that the patient can use to transport this study medication.

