11.1 Schedule of Evaluations

For the purposes of this study, patients should be re-evaluated every 6 weeks (every 2 cycles) for the first 8 cycles of treatment and then every 12 weeks (every 4 cycles) until progression.

For patients randomized to Arm 2 who crossover to Z-Endoxifen HCl, disease evaluations should occur every 6 weeks after starting Z-Endoxifen HCl for the first 8 cycles of treatment and then every 12 weeks until progression

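### Objective 2.2.2 asks whether tumor response differs between arms, but no between-arm estimate is planned; the 6-week confirmation rule also needs a stated tolerance

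*Combined protocol and SAP*

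**What the plan says.** **Comparison of arms.** Objective 2.2.2 is comparative: whether response on Z-endoxifen "differs from that among those randomized to tamoxifen". The matching analysis, section 13.1.6.2 (headed as by study arm), reads "A 90% binomial confidence interval will be constructed for the true response rate". It gives no difference, ratio, test or between-arm interval. The other analyses of response, in sections 13.2.2 and 13.2.4, contrast patients by tumor marker, within arm or with the arms pooled.

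**Confirmation rule.** Section 13.1.6.2 counts a patient as a responder if CR or PR is seen "on 2 consecutive evaluations at least 6 weeks apart".

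**Timing of scans.**
- Cycles last 21 days. Footnote * of sections 5.1 and 5.2 says that after cycle 1 "labs, scans, tests and observations may be obtained no more than +/- 3 days prior to day 1 of treatment".
- The dosing tables in 7.1 and 7.2 allow the cycle itself to move: "Every 21 days (+/- 3 days".
- Footnote E of 5.1 and 5.2 places scans "at completion of cycles 2, 4, and 6 (approximately, every 6 weeks) then every 4 cycles (approximately every 3 months".
- Section 11.1 has patients "re-evaluated every 6 weeks (every 2 cycles) for the first 8 cycles of treatment", and every 12 weeks after that.

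**The concern.** An objective that asks whether two rates differ needs an estimate of the difference. With only two separate intervals, readers will compare them by eye. That is a conservative and informal substitute, because two intervals can overlap when the interval for the difference excludes zero. The plan does name a between-arm test for PFS (13.1.5) and for the bone markers (13.4), so response is the exception.

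The confirmation rule is a smaller matter. Its minimum has no margin over the nominal early scan gap. Two analysts with the same data could report different numbers of confirmed responders, depending on whether they count days or scheduled visits. Supply is open label (10.1.1) and efficacy data go into semi-annual reports (13.1.7), so the choice is better fixed in writing before response is tabulated by arm.

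**Working it through.** **1. Difference in response rates**

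Inputs: 40 per arm (13.1.3) and the 90% level (13.1.6.2). The documents give no design response rates, so the counts and rates below are assumptions. Section 13.1.6.2 says only that the interval is binomial; Clopper-Pearson is used here.

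Take 8/40 (20%) and 2/40 (5%).
- By-arm 90% intervals: 10.4-33.2% and 0.9-14.9%. They overlap, since 10.4 < 14.9.
- Newcombe 90% interval for the difference. It uses Wilson limits with z = 1.645: 0.1165 to 0.3215 for 8/40, and 0.0167 to 0.1403 for 2/40.
  - Lower: 0.15 - √[(0.20 - 0.1165)² + (0.1403 - 0.05)²] = 0.15 - 0.123 = 0.027
  - Upper: 0.15 + √[(0.3215 - 0.20)² + (0.05 - 0.0167)²] = 0.15 + 0.126 = 0.276
- The difference is 15 points, with a 90% interval of 2.7 to 27.6.

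Full enumeration of two binomials with n = 40 gives:

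| Assumed true rates | By-arm intervals apart | Difference interval above 0 |
|---|---|---|
| 20% vs 5% | 26% | 66% |
| 20% vs 0% | 71% | 97% |
| 15% vs 0% | 39% | 87% |
| 10% vs 0% | 10% | 58% |

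The 0% rows take up the tamoxifen result after AI failure cited in section 1.3.4 ("the objective response rate was 0% and progression free survival 7.0 month"). With equal true rates, the difference interval lies above 0 in 2.2% (both 5%) and 4.1% (both 10%), so the gain does not come from a loose procedure. The mean width at 20% vs 5% is 24.6 points.

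**2. Confirmation gap**

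Nominal gap: 2 cycles × 21 days = 42 days = 6 weeks. This reproduces the 6-week interval of 11.1 and equals the minimum in 13.1.6.2, so the margin is zero.

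Actual gap = 42 + c1 + c2 + s2 - s1. Here c1 and c2 are the shifts of the two cycles, s1 and s2 are the offsets of the two scans, and each lies between -3 and +3 days.
- Scan window alone: 42 ± 6 = 36 to 48 days. If the calendar footnote allows scans only up to 3 days early, the range is 39 to 45 days.
- Scan and cycle windows: 42 ± 12 = 30 to 54 days.

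Share of 6-week pairs under 42 days. The documents give no scatter, so independence and the shapes are assumptions:

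| Chance that each shift is on day 0 | Scan window alone | Scan and cycle windows |
|---|---|---|
| 100% | 0% | 0% |
| 90% | 9.4% | 16.8% |
| 75% | 21.4% | 32.2% |
| 50% | 35.4% | 42.4% |
| 1/7 (uniform) | 21/49 = 42.9% | 1085/2401 = 45.2% |

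If a patient's scan offset is constant and cycles keep to 21 days, then s2 - s1 = 0, the gap is exactly 42 days and the pair passes.

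A failed pair is not yet a lost response. Under uniform scatter and the scan window alone, no pair qualifies in 42.9% of responses seen on two 6-weekly scans, 10.2% on three and 1.5% on four. Once a 12-week gap is included nothing is lost: the shortest such gap is 84 - 12 - 6 = 66 days.

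**3. End of 6-weekly scanning**

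Footnote E ends it after cycle 6, and 11.1 after cycle 8. Cycle 6 ends at week 18. A response first seen then is next scanned 12 weeks later under footnote E and 6 weeks later under 11.1.

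**The case against.** **On the comparison.** The by-arm counts will be reported, so anyone can calculate the difference; no information is lost. That is true, and what is missing is prespecification. A reader might also infer that the plan will judge the arms by whether their intervals overlap. No such rule is stated, so the 26% against 66% illustrates the gain from a direct estimate and is not the performance of a planned test.

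**On the 6 weeks.** The protocol itself uses the term nominally: 11.1 equates it with 2 cycles, and footnote E calls it approximate. Read that way, 13.1.6.2 rejects no compliant pair. This is a fair reading, but the rule is worded as a minimum and nothing ties it to the windows, so the text does not settle the matter.

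**On size.** A reader might infer from the upper figures that over 40% of responses would go unconfirmed, or that the arms would be biased against each other. The documents support neither. The figures are for pairs of scans and not for patients, they rest on assumed independent scatter, and they fall to zero when visits keep to the nominal day. Both arms have the same windows and schedule, and nothing suggests different timing by arm.

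**Conclusion.** The main point holds on the text: objective 2.2.2 is comparative and its analysis is not. The remedy uses data already collected. The resulting interval will be wide, about 25 points on average at assumed rates of 20% and 5% with 40 per arm, so it stays a secondary estimate.

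The confirmation point is real but conditional. It matters only if 6 weeks is counted in days. The share of pairs affected then lies anywhere from 0% to 43% (scan window alone) or 45% (both windows), depending on scatter that the documents do not describe. Lasting loss falls mainly on responses seen on only two 6-weekly scans, and the number of such patients is unknown.

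The conflict between footnote E and section 11.1 is plain. Overall this is minor: it concerns a secondary endpoint and leaves the PFS analysis unaffected.

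**What to change.** 1. **Section 13.1.6.2, comparison.** Add the between-arm difference in response rate with a 90% interval, for example Newcombe score, as a secondary estimate for objective 2.2.2. Keep the by-arm rates and the planned denominator.

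2. **Section 13.1.6.2, confirmation.** By dated amendment, state that two consecutive evaluations showing CR or PR confirm a response if they are at least 42 days apart, or if they are consecutive scheduled evaluations two or more cycles apart, both within the protocol windows. Both routes are needed. Requiring scheduled, in-window scans alone would drop late or unscheduled confirmations at 42 days or more that count today.

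3. **Sections 5.1, 5.2 and 11.1.** Reconcile when 6-weekly scanning ends.

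Cost: items 1 and 2 change wording only, with no new data and no extra scans. The price of item 2 is that some confirmations may rest on a gap as short as 30 days. Section 13.1.3 shows that enrolment was already under way. If response has been tabulated by arm before the amendment, the amendment should say so, and the responder counts under the literal 42-day rule and under the amended rule should both be reported.
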